Hypothesis 3: The use of both BoNT-A injections and supervised gait retraining will be more effective than either treatment alone. In adult active duty service members with CECS, the use of both BoNT-A injections and supervised gait retraining returns service members to full duty, including being able to complete their service-specific military physical tests, sooner and for sustained longer periods than SGR or BoNT-A injections alone.

Process for Hypothesis 3: Evaluate functional improvements in Group 4 as compared to Groups 2 & 3 via the subjective and objective data variables described in protocol sections 10.1 & 10.2. Assess the ability of all study groups to complete a 2-mile run and to compete their required service-specific physical fitness testing within the established standards at 8 weeks, 3 months, 6 months, and 12 months post-study injection.

9.4 Study Design:

Describe study design in one to two sentences (e.g., prospective, use of existing records/data /specimens, observational, cross-sectional, interventional, randomized, placebo-controlled, cohort, etc.). Specify the phase – Phase I, II, III, or IV – for FDA-regulated investigational drug research

Multi-site, single-blinded randomized placebo-controlled study

9.5 Target Population:

Describe the population to whom the study findings will be generalized

Adult military beneficiaries diagnosed with Chronic Exertional Compartment Syndrome (CECS)

9.6 Benefit to the DoD:

State how this study will impact or be of benefit to the Department of Defense

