At 8 weeks (+/- 1 week), 3 months (+/- 2 weeks), 6 months (+/- 2 weeks), and 12 months (+/- 2 weeks) post-injection, participants will undergo Balance Error Scoring System (BESS) testing, objective foot parameters, ankle strength, range of motion (ROM), ankle brachial index (ABI) blood pressure, and palpation tests, and a gait and run analysis using advanced wearable technology as part of a self-paced treadmill test until cessation or the successful completion of a two-mile run (whichever occurs first). A gait analysis Data Collection CRF (Appendix R) will be used to collect some of the gait analysis from the advanced wearable technology and will be completed after the participant's visit.

Participants will also be asked about involvement in non-study related activities and treatments including acupuncture/acupressure, aquatics, anti-inflammatory/pain medication, athletic taping, change in running shoes, chiropractor, dry needling, electrical stimulation, foot orthotics, gait retraining, ice pack/massage, massage, physical therapy, strengthening, stretching, yoga, and other treatments.

Intramuscular compartment testing of participant's anterior and lateral compartments will be re-tested at 6 months (+/- 2 weeks) post-injection. The same compartments tested at baseline or at a previous test 6 months prior to consent of the study, will be recollected at the 6 month time point.

Results of the in-person clinical assessments and the intramuscular compartment testing will be recorded in the Follow Up Data Collection CRF.

Overall, the 8 week, 3 month, 6 month, and 12 month follow up activities will take approximately 2.5 hours each and the 24 month follow up activities will take approximately 30 minutes each.

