Blinding will be revealed to the participants after all the components of the 3 month follow-up visit have been completed. Participants who are not satisfied with their treatment results and/or who are unable to complete a 2-mile run without producing pain and/or symptoms will be offered the option to receive BoNT-A injections and/or Supervised Gait Retraining if they had not received those active treatments.

At the 6 month follow-up visit, participants who are still not satisfied with their treatment results and/or still unable to complete a 2-mile run will be offered any remaining treatment option, including surgical fasciotomy which is offered as standard of care. Participants who express interest in surgical fasciotomy will be referred to an orthopaedic surgeon who will dictate and guide this treatment option. Further details and scheduling will be per the orthopaedic surgeon's recommendations. Patients who cross over to alternative treatment options (including surgical fasciotomy) will remain in the study and will continue to follow up with the research team at the intervals listed above.

Data Entry:

With the exception of the Intake CRF which collects participant contact information, all coded research data will be entered into REDCap, an encrypted, access controlled, password protected electronic data capture and management system housed on a DoD server and maintained by the Uniformed Services University (USU). No PII will be entered into REDCap. See Appendix J for additional information on REDCap. See Appendix I for a PDF copy of the REDCap forms for this study.

Additional Info - MIRROR/USU:

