Secondary outcomes will include pain reduction according to the Numeric Pain Rating Scale (NPRS), ability to complete service specific military physical training requirements, and patient satisfaction. To assess patient satisfaction, patients will be asked if they were or were not satisfied with intervention at each follow up time point.

This will be an intention to treat study and additional data that will be collected via the Demographics CRF (Appendix C) and Baseline Data Collection CRF (Appendix D) includes:

- Standard Demographics (e.g., Age, Sex, military occupational specialty, height, weight, BMI, MOS)
- Length of military service
- Symptom duration (including length of limited duty, military profile)
- Previous Treatments
- Time to diagnosis

- Concomitant medical conditions
- Footwear characteristics and orthosis use
- Activities provoking symptoms, and perceived exertion (Borg) tolerance
- Duration of symptoms when present
- Performance on military fitness tests
- Ability to perform occupational related tasks
- Objective lower extremity strength, range of motion (ROM), ankle brachial index (ABI) blood pressure, palpation, leg length, foot parameters tests

10.3 At any point in the study, will you request, use, or access health information in any form, including verbal, hard copy and electronic?

☒ Yes ☐ No

10.4 Review the definitions below and respond to the following two questions. If you are not sure of the answers, email [contact] for assistance. The *Military Health System (MHS)* is defined as all DoD health plans and DoD health care providers that are organized under the management authority of, or in the case of covered individual providers, assigned to or employed by, the Defense Health Agency (DHA), the Army, the Navy, or the Air Force. *MHS workforce members* are employees, volunteers, trainees, and other persons whose conduct, in the performance of work for the MHS, is under the direct control of the MHS, whether or not they are paid by the MHS. *MHS business associates* are persons or entities that provide a service to the MHS and require protected health information (PHI) to provide the service.

Are you an MHS workforce member?

- ☒ Yes, I am an MHS workforce member
☐ No, I am not an MHS workforce member

10.5 Have you consulted with an MHS data expert to determine the data elements required for your study?

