11.5 Please provide a justification for your sample size

Using a 2x2 factorial design and assuming success rates for passing the US Army 2-mile run test among control (saline/home based gait retraining), botulinumtoxin A (BoNT-A) injection, supervised gait retraining (SGR), and combined therapy (BoNT-A + SGR), respectively, are 15%, 80%, 50%, and 85%, we estimate that enrolling a grand total of at least 60 patients would yield 80% power to detect the effect of BoNT-A, enrolling a grand total of at least 120 patients would yield 80% power to detect the effect of SGR, and enrolling a grand total of at least 380 patients would yield 80% power to demonstrate the benefit of combined therapy (BoNT-A + SGR) vs. either therapy in isolation. If we can obtain complete data on more than 380 participants, then it will strengthen our power. We hope to have a final sample of 480 participants. Assuming roughly 20% attrition and accounting for screen failures, we are requesting to enroll up to 620 participants across all performance sites.

Power was estimated using Monte Carlo simulations assuming uniform randomization among four groups in the 2x2 factorial design, while testing for statistical significance simultaneously among the four groups of control, BoNT-A, SGR, and combined therapy using a generalized linear model. Statistical significance was indicated if the corresponding $p < 0.05$ per generalized linear model.

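### No primary time point is set, and from 6 months the intention-to-treat contrasts compare strategies with rescue allowed, not the treatments named in the hypotheses

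*Combined protocol and SAP*

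**What the plan says.** Section 9.3 compares Group 3 with Group 1 (Hypothesis 1), Group 2 with Group 1 (Hypothesis 2), and Group 4 with Groups 2 and 3 (Hypothesis 3). Hypothesis 3 claims a return to duty that is both faster and longer lasting. Its process assesses the 2-mile run and the service fitness test "within the established standards at 8 weeks, 3 months, 6 months, and 12 months post-study injection". Hypotheses 1 and 2 give no visit. They refer to the variables of 10.1 and 10.2, which are collected to 12 months, with questionnaires again at 24 months. No section names a primary time point.

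Section 10.2 says "This will be an intention to treat study", and 11.1 specifies complete-case intention to treat.

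Under Study Blinding in 10.1, "Blinding will be revealed to the participants after all the components of the 3 month follow-up visit have been completed". Participants who are dissatisfied and/or cannot run 2 miles without symptoms then "will be offered the option to receive BoNT-A injections and/or Supervised Gait Retraining if they had not received those active treatments". At the 6-month visit, those still dissatisfied or unable to run are offered whatever remains, including fasciotomy. Participants who cross over stay in follow-up.

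Sections 11.1 to 11.5 mention neither crossover nor fasciotomy, and they do not restrict the analysis to any visit.

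**The concern.** Crossover is triggered by failure, and failure is what the treatments are meant to prevent. Uptake will therefore differ by arm by design: most of Group 1 may qualify and few of Group 3. Group 4 has no study treatment left to be offered at 3 months. A 6- or 12-month comparison by assigned group then sets partly rescued controls against the active arm.

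Two things are at stake. A diluted 12-month result could be read as a treatment that does not work or does not last. And with four assessment times and no primary one, the visit that carries the conclusion could be chosen after the data are seen. The durability part of Hypothesis 3 is the most exposed, because it rests entirely on visits after crossover opens.

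**Working it through.** **Inputs from the documents.** Section 11.5 assumes 2-mile-run success of 15% (Group 1, control), 50% (Group 2, SGR), 80% (Group 3, BoNT-A) and 85% (Group 4, combined), with significance at p < 0.05. Section 11.2 gives 120 evaluable per group.

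**The plan's own figures.** Section 11.5 states that "enrolling a grand total of at least 60 patients would yield 80% power to detect the effect of BoNT-A", with 120 in total for SGR and 380 for combined therapy against either alone. Simulating the planned logistic model (three group indicators, two-sided Wald test) gives:
- 60 in total, Group 3 v 1: power 0.74 to 0.81, consistent with the claim.
- 120 in total, Group 2 v 1: 0.81 to 0.83, consistent.
- 380 in total: Group 4 v 2 above 0.99, but Group 4 v 3 only 0.14 to 0.15. The 380 figure is not reproduced. That is a separate matter and the present point does not rest on it.

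None of these figures allows for crossover.

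**Who qualifies at 3 months.** The plan's rates carry no visit, so I take them as 3-month rates and let run failure stand in for the crossover criterion. Failures per 120 are:
- Group 1: 0.85 × 120 = 102
- Group 2: 0.50 × 120 = 60
- Group 3: 0.20 × 120 = 24
- Group 4: 0.15 × 120 = 18, with no study treatment left to be offered

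**Later success rates.** Let u be the share of eligible participants who accept all missing active treatment. Assume full uptake brings a group to the 85% combined rate: later rate = p + u × (0.85 − p). So Group 1 = 0.15 + 0.70u, Group 2 = 0.50 + 0.35u, Group 3 = 0.80 + 0.05u and Group 4 = 0.85. Differences are in percentage points, with two-sided power at 120 per arm in brackets:

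| Uptake | 3 − 1 | 2 − 1 | 4 − 2 | 4 − 3 |
|---|---|---|---|---|
| 0% | 65 (>0.99) | 35 (>0.99) | 35 (>0.99) | 5 (0.17) |
| 25% | 48.8 (>0.99) | 26.3 (0.99) | 26.3 (>0.99) | 3.8 (0.12) |
| 50% | 32.5 (>0.99) | 17.5 (0.79) | 17.5 (0.90) | 2.5 (0.08) |
| 75% | 16.3 (0.84) | 8.8 (0.33) | 8.8 (0.40) | 1.3 (0.05) |
| 100% | 0 | 0 | 0 | 0 |

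**Sensitivity to switchers' success.** Now let each switcher in Groups 1 to 3 succeed with a fixed probability s, so later rate = p + (1 − p) × u × s:

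| s | Uptake | 3 − 1 | 2 − 1 | 4 − 2 | 4 − 3 |
|---|---|---|---|---|---|
| 0.425 | 50% | 51.2 | 27.6 | 24.4 | 0.8 |
| 0.425 | 100% | 37.4 | 20.1 | 13.8 | −3.5 |
| 0.85 | 50% | 37.4 | 20.1 | 13.8 | −3.5 |
| 0.85 | 100% | 9.8 | 5.3 | −7.5 | −12 |

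Shrinkage of 3 − 1, 2 − 1 and 4 − 2 appears in every row. The sign of 4 − 3 depends on the assumption.

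**The case against.** **The later contrasts are still valid.** An intention-to-treat comparison at 6 or 12 months is a sound randomised comparison of strategies: start with one treatment, and allow a switch after 3 months. That stands. It is not, however, the comparison the hypotheses state. The 8-week and 3-month contrasts, and most of the claim of a faster return, are untouched.

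**The effect may be modest.** At 50% uptake, 3 v 1 keeps power above 0.99, 2 v 1 has 0.79 and 4 v 2 has 0.90. The 4 v 3 contrast had only 0.17 at 120 per arm with no crossover at all. This also stands: the damage depends on uptake, which the documents do not give.

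**Stronger readings that a reader might infer but that the documents do not support:**
- *Effective treatments will look reversed.* For 3 v 1 and 4 v 2 this needs near-complete uptake and selected failures responding like unselected patients. With 80% success among switchers and Groups 3 and 4 held fixed, full uptake gives Group 1 = 0.15 + 0.85 × 0.80 = 83% and Group 2 = 0.50 + 0.50 × 0.80 = 90%, hence −3 and −5 points. But that puts Group 1 above the plan's own BoNT-A rate and Group 2 above its combined rate.
- *The bias falls hardest on Group 4's comparisons.* In points, 3 v 1 loses most (32.5 at 50% uptake in the main illustration, against 17.5 for 4 v 2 and 2.5 for 4 v 3). Only 4 v 3 stands out, because it is small enough to vanish or change sign.
- *Unblinding compromises every later comparison.* Only the injection is blinded. Groups 3 and 4 share BoNT-A, Groups 1 and 2 share saline, and SGR against home training is never described as blinded. The added reporting bias mainly concerns self-reported outcomes in 3 v 1 and 4 v 2.
- *The pressure endpoint is lost.* The anterior and lateral "compartments will be re-tested at 6 months (+/- 2 weeks) post-injection", after crossover opens, but 10.2 does not list pressure among the outcomes. The point is peripheral.

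**Conclusion.** The concern holds. The plan sets no primary time point and no rule for crossover, while its hypotheses are assessed on data collected well after rescue opens. From 6 months the planned contrasts estimate the effect of assigned strategies with rescue, and the main consequence is dilution. In the main illustration, 50% uptake halves every contrast and full uptake removes them. The 4 v 3 contrast can vanish or reverse under some assumptions. The durability part of Hypothesis 3 cannot be answered by these contrasts as planned.

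The sizes rest on assumptions that the documents do not supply: uptake, success after switching, and run failure as a proxy for eligibility. Eligibility also counts dissatisfaction and symptoms, so it could be higher. Groups are otherwise held constant over time. The retrospective review in 9.2 reports a mean of 7.8 months of improvement among patients whose symptoms recurred after BoNT-A. A crossover injection would be at most about 12 − 3 = 9 months old at the 12-month visit, which could narrow 3 v 1 and 4 v 2 further. The structural finding does not depend on any of these figures.

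**What to change.** Amend 9.3, 10.2 and 11.1 as follows.

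1. Name the 3-month visit, completed before unblinding and crossover, as the primary time point for Hypotheses 1 to 3.
2. Label the 6-, 12- and 24-month intention-to-treat contrasts as secondary comparisons of assigned strategies with crossover allowed. Report crossover and fasciotomy counts by arm beside them.
3. For the durability part of Hypothesis 3, pre-specify one supportive analysis applied identically in all arms: success at 3 months and at each later visit without added study treatment or fasciotomy. This is preferable to setting post-crossover data to missing and imputing. Because failure triggers the switch, at high uptake few unswitched failures remain to impute from.
4. State one limit of that analysis. A participant who passes the run but is dissatisfied can take added study treatment in Groups 1 to 3 and would then count as a failure. In Group 4 no such treatment remains at 3 months.

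The crossover offer, the visits and the sample size are unchanged, so the cost is wording. The price is that durability beyond 3 months becomes a secondary, supportive claim.

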A newer proposed treatment for CECS is the intramuscular administration of botulinum toxin A (BoNT-A) into the muscles of the involved compartment(s). BoNT-A is FDA approved for intramuscular, intradetrusor, or intradermal use for muscle spasticity, migraine headaches, detrusor instability and severe forehead lines, lateral canthal lines, and glabellar lines in adults. A 2013 case series studying botulinum toxin injections for CECS demonstrated normalized intramuscular pressure up to nine months post-injection in 87.5% (14/16) of patients, and exertional pain was completely eliminated in 94% (15/16) of patients. Eleven patients experienced reduced muscle strength that was without functional consequences and transient resolving within 3 months. Only 1 of the 16 patients complained of new posterior leg pain that did not appear to be related to BoNT-A injections. There were no other adverse effects reported.¹ An additional 2016 case report showed effective pain and paresthesia relief from CECS after 1 set of injections for a recreational female athlete. In this report, the patient's symptoms resolved within 1 week. More importantly, she was able to return to full recreational activity within 4 weeks, with no return of symptoms throughout the 14 months of follow up without any weakness or adverse effect.²

Military sports medicine clinics at Fort Belvoir Community Hospital (FBCH) and the Uniformed Services University (USU) as well as the Department of Physical Medicine & Rehabilitation at Walter Reed National Military Medical Center WRNMMC) currently utilize BoNT-A (trade names BOTOX® or Xeomin®) injections for the non-surgical treatment of CECS. All of our performance sites currently offer BoNT-A (trade names BOTOX® or Xeomin®) injections as standard of care non-surgical treatment options for CECS.

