Those randomized into the normal saline groups will receive injections in the identical manner above, using the appropriate amount of solution (0.5 mL to 1 mL). The syringes will be prepared by the clinical research staff using standard sterile techniques, out of view of the participant to ensure appropriate blinding.

Study Injection Documentation (both groups):

All injections will be done under ultrasound guidance. The provider will use the ultrasound machine to identify bony landmarks of the tibial plateau and will then move the probe laterally towards the fibular head to identify the anterior and lateral compartments of the lower leg. Distally, the provider will identify the midway area between the fibular head and the tip of the lateral malleolus.

Study injection administration to the participant will be documented using a Treatment Documentation CRF (Appendix N). This Treatment Documentation CRF will be entered into REDCap. Study injection administration will also be documented in the participant's electronic medical record following standard procedures.

Supervised Gait Retraining (SGR):

The SGR course will focus on mid-forefoot strike, increasing their cadence while shortening their stride, and decreasing their peak ground reaction force. This program has been developed by physical therapists at West Point and the Army DPT program in Fort Sam Houston. This program uses group physical therapy sessions, lower extremity exercises, home exercise training drills, and advanced wearable technology to effectively change key gait parameters.

Supervised physical therapy sessions will be documented using a SGR Physical Therapy Documentation CRF (Appendix M). This SGR Physical Therapy Documentation CRF will be entered into REDCap. Study supervised physical therapy sessions will also be documented in the participant's electronic medical record following standard procedures. Participants in the SGR group(s) will also be sent home with a handout (Appendix L) explaining exercises that can/should be done from home to supplement their supervised physical therapy sessions.

Home Based Gait Retraining:

The HBGR will focus on increasing cadence, running softer and increasing endurance strength with exercises for the lower extremity. A handout (Appendix L) explaining desired exercises and gait retraining will be given to each participant with daily exercise instructions. Participants will be contacted weekly as a reminder to complete their home program.

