For participants assigned to the HBGR group, their first (and only) study-related in-person physical therapy session and follow up communications will be documented using an HBGR Physical Therapy Documentation CRF (Appendix Q). This HBGR Physical Therapy Documentation CRF will be entered into REDCap. Their first (and only) study-related in-person physical therapy visit will also be documented in the participant's electronic medical record following standard procedures.

Both the SGR & HBGR Groups:

Initiation of physical therapy visits for both SGR and HBGR groups can be greater than or equal to 2 weeks post-injection. All participants (regardless of study arm) will be instructed to avoid other physical therapy and invasive treatments (including acupuncture) while participating in this study. Concomitant medications and therapies will be recorded at each follow up visit (Appendix M & Appendix Q). Participants will be free to participate in optional complimentary activities available to them as standard of care such as aquatics and yoga.

Follow Up Data Collection:

For all study groups, participants will complete a Follow Up Data Collection CRF (Appendix E) at 8 weeks (+/- 1 week), 3 months (+/- 2 weeks), 6 months (+/- 2 weeks) and 12 months (+/- 2 weeks) post-study injection and a Long Term Follow Up Data Collection CRF (Appendix F) at 24 months (+/- 4 weeks) post injection. The Follow Up Data Collection CRF and Long Term Follow Up Data Collection CRF both include the following measures: Numeric Pain Rating Scale (NPRS), University of Wisconsin Running Injury and Recovery Index (UWRI), Single Assessment Numerical Evaluation (SANE), Patient Specific Functional Scale (PSFS), and the Global Rate of Change (GROC). Additionally, patients will be asked about their ability to complete their service-specific military physical training requirements, running and activity leg symptoms, footwear characteristics and orthosis use, pertinent medical history, and treatment satisfaction at each follow-up time point.

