The potential side effects of Botulinum toxin A injections include: rare minor side effects of bleeding, pain, soreness, infection, transient general muscle weakness and muscular atrophy, flu-like symptoms, and even rarer transient breathing and swallowing difficulties which has the potential to cause death if not appropriately treated.

The potential side effects of saline injections include: pain, soreness, bleeding, and infection which are all very rare.

The potential side effects of IMCP needle insertion for intramuscular compartment pressure testing include: pain which is minimized with local anesthesia, soreness, minor local bleeding, and the rare incidence of infection.

The potential risks for balance screening, physical objective measurements, physical performance based testing, gait retraining, standard gait analysis, self-paced treadmill test, and lower strengthening and stretching exercises include: physical discomfort (increased pain and reduced activity level), soreness, possible chronic or acute musculoskeletal injury, overuse or a fall.

Any time information is collected for a study, there is a small risk of breach of confidentiality.

14.2

Measures to Minimize Risks of Harm (Precautions, safeguards):

For each research procedure or intervention, describe all measures to minimize and/or eliminate risk of harms to subjects and study personnel

All available precautions will be taken to minimize the above-mentioned risks. Standard clinic protocols will be followed to reduce the risks of infections and related complications.

To minimize the risk to participants, once they receive their injection, a waiting period of at least 15 minutes will occur at the clinic. This waiting period is to observe for any side effects that may occur due to the injection. The participant will also be given an after care injection handout. In order to safeguard participants, providers will use ultrasound guidance to identify the locations of the anterior and lateral compartments of the lower leg. Expected soreness may occur from the study injection procedures which may impact the start of physical therapy visits to 2 weeks post injection. Providers will be trained on all study procedures. All of this will provide consistent delivery of treatment to the targeted areas and minimize risk to the participant.

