In order to protect participant confidentiality, research data will be identified using a unique study ID only, and not by participant name, date of birth, social security number, DoD ID, or other similar identifier. All available measures allowed by law will be taken by research staff to protect participant confidentiality. See protocol section 14.3 for additional information.

All participants will be evaluated for adverse events at each follow-up visit and concomitant medications and treatments will be documented. All adverse events, regardless of severity, will be reported to the Principal Investigator and Research Medical Monitor. The Research Medical Monitor will review all adverse events. Adverse events will also be reported according to the guidelines stated in Protocol Section 16.

14.3

Confidentiality Protections (for research records, data and/or specimens):

Describe in detail the plan to maintain confidentiality of the research data, specimens, and records throughout the study and at its conclusion (e.g., destruction, long term storage, or banking). Explain the plan for securing the data (e.g., use of passwords, encryption, secure servers, firewalls, and other appropriate methods). If data will be shared electronically with other team members/collaborators outside the institution, describe the method of transmission and safeguards to maintain confidentiality. Explain whether this study may collect information that State or Federal law requires to be reported to other officials or ethically requires action, e.g., child or spouse abuse

Upon consenting for the study, participants will be assigned a unique study ID. With the exception of the Informed Consent Form, HIPAA Authorization, Intake CRF (Appendix B) and electronic Master List, all research data (both paper and electronic) will be identified using this unique study ID only, and not by the participant's name, date of birth, social security number, DoD ID, or other protected identifier.

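### Visits after a crossover BoNT-A injection stay on the original calendar, so adverse events are not collected as they are for randomised recipients

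*Combined protocol and SAP*

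**What the plan says.** **Visit clock.** Section 10.1 (Follow Up Data Collection) sets the follow-up forms at "8 weeks (+/- 1 week), 3 months (+/- 2 weeks), 6 months (+/- 2 weeks) and 12 months (+/- 2 weeks) post-study injection", with a questionnaire at 24 months. The in-person assessments at the first four of these visits include ankle strength. Section 14.2 ties safety collection to the same visits: "All participants will be evaluated for adverse events at each follow-up visit".

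**Crossover.** Section 10.1 (Study Blinding) unblinds participants once the 3-month visit is complete. Those who are dissatisfied, or who cannot run two miles free of symptoms, "will be offered the option to receive BoNT-A injections and/or Supervised Gait Retraining if they had not received those active treatments". At 6 months, those still dissatisfied or unable to run are offered whatever treatment remains, fasciotomy included. Participants who cross over stay in the study and "will continue to follow up with the research team at the intervals listed above".

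**Known effect of the drug.** Section 9.2 says of the 16-patient case series: "Eleven patients experienced reduced muscle strength that was without functional consequences and transient resolving within 3 months". Section 9.6 mentions self-limited ankle dorsiflexion weakness in the sponsor's retrospective review of 29 patients.

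**Risk wording.** Section 14.1 lists "rare minor side effects of bleeding, pain, soreness, infection, transient general muscle weakness and muscular atrophy" for BoNT-A. The section 18.2 entries for both products are worded in nearly the same way.

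**The concern.** A participant randomised to BoNT-A is seen at 8 weeks and at 3 months after the injection. A saline participant who takes BoNT-A later receives the same drug but keeps a calendar that counts from the saline injection. The next scheduled visit then comes at an interval that depends on when the crossover injection happened to be given. Reduced strength, the effect that the plan's own source reports most often, had resolved by 3 months in that source, so the timing of visits decides whether it is examined while present.

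Two things are at stake. First, event rates from randomised and crossover injections could not be compared or pooled cleanly, because they would be collected on different schedules. Second, section 10.2 declares an intention-to-treat study and the plan does not describe an adverse event table. If events were summarised by assigned arm only, BoNT-A events in crossovers would be counted under saline. This is a point about harms, separate from what crossover does to the efficacy comparison.

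**Working it through.** The plan gives neither the number nor the timing of crossover injections, so it has no figure of its own to reproduce.

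**Inputs**
- Visit times and windows: section 10.1 (8 weeks ±1 week; 3, 6 and 12 months ±2 weeks).
- Assumed success on the Army 2-mile run: 15% in Group 1 and 50% in Group 2 (section 11.5).
- Final sample: 120 per group (section 11.2).
- Reduced strength in 11 of 16 patients, resolved within 3 months (section 9.2).
- Uptake *a* of crossover BoNT-A among saline-arm run failures: not in the documents. Assumed range 25% to 100%.

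**Step 1: time from injection to next visit.** One month is 365.25/12/7 = 4.35 weeks, so 3, 6 and 12 months are about 13.0, 26.1 and 52.2 weeks.
- Randomised to BoNT-A: 8 weeks (7 to 9) and 13 weeks (11 to 15). Two looks.
- Crossover injected at the month-3 visit: 26.1 − 13.0, about 13 weeks. Shortest with windows: (26.1 − 2) − (13.0 + 2), about 9. Longest: (26.1 + 2) − (13.0 − 2), about 17. One look, near the elapsed time of the randomised recipient's second.
- If that injection is given *d* weeks after the month-3 visit, the month-6 visit falls about 13 − *d* weeks after it. It lands at 7 to 9 weeks only if *d* is about 4 to 6. The plan sets no window for crossover injections.
- Crossover injected at the month-6 visit: 52.2 − 26.1, about 26 weeks. Shortest: (52.2 − 2) − (26.1 + 2), about 22. Longest: (52.2 + 2) − (26.1 − 2), about 30. The month-12 visit would fall within 3 months of the injection only if the injection were delayed by about 26 − 13 = 13 weeks or more.

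**Step 2: compare with the period of weakness.** The cited rate is 11/16 = 69% (exact 95% interval 41% to 89%), all resolved within 3 months. Month-3 crossovers have one look near the end of that period, or inside it if injected later. Month-6 crossovers injected promptly have none.

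**Step 3: share of BoNT-A exposures.** With *n* per group, randomised exposures are 2*n* (Groups 3 and 4). Crossover exposures are *a* × *n* × [(1 − 0.15) + (1 − 0.50)] = 1.35*an*. The share is 1.35*a*/(2 + 1.35*a*), which does not depend on *n*.
- *a* = 100%: 102 + 60 = 162 at 120 per group; 162/(162 + 240) = 40.3%.
- *a* = 75%: 121.5/361.5 = 33.6%.
- *a* = 50%: 81/321 = 25.2%.
- *a* = 25%: 40.5/280.5 = 14.4%.
- If every saline participant crossed over: 240/480 = 50%.

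**Step 4: risk wording side by side.** Sections 14.1 and 18.2 name only generalised weakness and place it among rare effects. Sections 9.2 and 9.6 report reduced strength in 11 of 16 patients and local weakness at the ankle. These are not the same event. The local effect, which the plan's own background documents, is missing from the lists.

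**The case against.** **The anchor is inferred.** It follows from the instruction to carry on at the same intervals and from silence about any restart. There is no explicit rule, and Appendices E, H and N were not available. This stands, and it is a reason to state the intention.

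**Crossovers are not unmonitored.** A reader might infer that the trial will miss their harms. The documents do not support that. There is a 15-minute observation after injection (14.2), all adverse events go to the investigator and the monitor (14.2, 16.1), and clinical notes are collected throughout participation (10.14). The month-6 and month-12 visits include ankle strength. Nothing limits adverse event questions to events present on the day, so a resolved event can still be reported. What is lost is scheduled assessment in the relevant period. The effect at issue was transient and without functional consequences in the cited series.

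**The 40% is near the top of the range.** It assumes that every saline-arm run failure takes BoNT-A, although a Group 1 failure may choose supervised gait retraining alone. The success rates have no stated time point and concern passing a run test, whereas the crossover trigger is dissatisfaction or a symptomatic run. Dissatisfied participants who pass also qualify, which works the other way. The range should be quoted, not the single figure.

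**Two further inferences fail.** One is that participants are told a common effect is rare: the consent text and the after-care handout (Appendix O) were not available, and section 14.1 cannot show what they say. The other is that the monitoring in section 15.1 starts from a wrong expected rate: that section states none.

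**Conclusion.** The point holds as a gap in scheduled safety assessment that is cheap to close. Followed as written, a month-3 crossover injected at once gets one look at about 13 weeks instead of looks at 8 weeks and 3 months. A month-6 crossover is first seen at about 26 weeks, after the period in which the cited series saw reduced strength. Only the month-6 group misses that period entirely, and the documents give no basis for estimating its size.

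Crossovers of both kinds may make up about 14% to 40% of BoNT-A exposures. This rests on an assumed uptake of 25% to 100% and on the section 11.5 success rates standing in for crossover need. The consequence is that event rates would not be comparable between crossover and randomised injections, and that a summary by assigned arm alone would place crossover BoNT-A events under saline.

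The risk wording is a separate and smaller matter. It would go too far to say that 69% contradicts the word rare, because the lists speak of general weakness and the cited sources of reduced strength and local ankle weakness. The passages need to be reconciled.

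**What to change.** 1. **Sections 10.1 and 14.2.** State that each crossover BoNT-A injection is recorded, with its date, on the Treatment Documentation CRF (Appendix N). Send a short adverse event and weakness questionnaire 8 weeks and 3 months after it, by the existing REDCap survey link or by phone. If a restart of the visit schedule is already intended, say so.
2. **Section 11.1.** Add an adverse event table by injection last received and time since that injection, alongside the table by assigned arm. Label the crossover rows as open label, since participants are unblinded after month 3.
3. **Sections 14.1 and 18.2.** Reconcile the lists of effects with sections 9.2 and 9.6, so that the reduced strength seen in 11 of 16 patients and the ankle dorsiflexion weakness are accounted for.

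The existing home-programme calls should not be relied on for item 1. Section 10.1 says "Participants will be contacted weekly as a reminder to complete their home program", but the length of the programme is not stated, and nothing shows that these calls, or the supervised sessions, are still running after a month-3 or month-6 injection.

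The cost is protocol wording, one short form, one extra table and two brief remote contacts per crossover participant: at most about 2 × 162 = 324 contacts at 120 per group, if every saline-arm run failure takes BoNT-A and no one else does. No clinic visit is added, and no dose or treatment rule changes.
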